### **13.3 Informed Consent Form**

No study procedure may be implemented prior to obtaining a signed and dated written Informed Consent Form (ICF) from the subject or the subjects legally authorized representative. IRB review and approval are required for the ICF. The final IRB-approved ICF must be provided to FibroGen for regulatory purposes.

If there are any changes to the Sample ICF during the subjects' participation in the study, the revised ICF must receive the IRB's written approval before use and subjects must be re-consented to the revised version of the ICF.

### **13.4 Subject Confidentiality**

Release of research results should preserve the privacy of medical information and must be carried out in accordance with Department of Health and Human Services Standards for Privacy of Individually Identifiable Health information, 45 CFR Parts 160 and 164, and the HIPAA.

Subject medical information obtained as part of this study is confidential and may only be disclosed to third parties as permitted by the Informed Consent and HIPAA Authorization Form signed by the subject, or unless permitted or required by law. The subject may request in writing that medical information be given to his/her personal physician.

## **14 INVESTIGATOR REQUIREMENTS**

The Investigator must be medically qualified to directly supervise the conduct of the trial at his or her site. The Investigator agrees to employ qualified staff to participate in the trial. The Investigator will permit trial-related monitoring, audits, IRB review, and regulatory inspection(s), providing direct access to source data/documents.

### **14.1 Study Medication Accountability**

All Study Drug required for completion of this study will be provided by FibroGen. The recipient will acknowledge receipt of the drug by returning the appropriate documentation form indicating shipment content and condition. Damaged supplies will be replaced.

Accurate records of all Study Drug received, dispensed, returned, and disposed of by the study site according to the Study Reference Manual should be recorded using the Drug Inventory Log.

### **14.2 Disclosure of Data**

Data records generated by this study must be available for inspection upon request by representatives of the FDA or other regulatory agencies, national and local health authorities, FibroGen monitors/representatives and collaborators, auditors, and the IRB for each study site.

### **14.3 Study Files and Retention of Records**

The Investigator must maintain adequate and accurate records to enable the conduct of the study to be fully documented and the study data to be subsequently verified. These documents should be classified into at least the following two categories:

- (1) Investigator's Study Files, and
- (2) Subject Clinical Source Documents.

The Investigator's Study File commonly contains essential documents, which are defined as those documents that individually and collectively permit evaluation of the conduct of the study and the quality of the data produced. Examples of such essential documents are as follows: the protocol, amendments, CRFs and query forms, IRB approvals correspondence, informed consents, drug records, staff curriculum vitae, laboratory accreditation, authorization forms, and other appropriate documents and correspondence.

Subject clinical source documents (usually defined by the project in advance to record key efficacy/safety parameters independent of the CRFs) would include (although not be limited to) the following: subject hospitalization records, physician's and nurse's (or other study staff's) notes, appointment book, original laboratory reports, ECGs, x-rays, pathology and special assessment reports, consultant letters, screening and enrollment eligibility documentation, screening and enrollment logs, etc.

The Investigator shall retain records required to be maintained under 21 CFR 312.62(c) for a period of 2 years following the date a marketing application is approved for the drug for the indication for which it is being investigated. If no application is to be filed or if the application is not approved for such indication, the Investigator shall retain these records until 2 years after the investigation is discontinued and the FDA is notified.

If the Investigator moves or retires, he or she should identify in writing, the designee who will be responsible for record keeping. Archived data may be retained on electronic records or similar medium provided that a back-up exists and a hard copy is obtainable if required. No records will be destroyed without the prior written consent of FibroGen.

## **15 PUBLICATION POLICY**

A detailed explanation of FibroGen's publication policy is described in the Clinical Trial Agreement.

## **17 APPENDICES**

**Appendix 1. Schedule of Assessments – Randomized Treatment Phase**

Study Period	Screening Period (up to 6 weeks)		Treatment Period																	
	1	2 a	3	4	5	6	7	8	9	10	11	12	13	14	15	16	17	18	19	
Study Days			Day 1 pre dose	Day 1 post dose																
Study Week (± 3 day window for Week 3 to Week 48)	Scr 1	Scr 2 a	0	0	3	6	9	12	15	18	21	24	27	30	33	36	39	42	45	48
Signed and Dated Written Informed Consent	X																			
Inclusion/ Exclusion Criteria	X																			
Demographics	X																			
Medical History	X																			
SGRQ			X					X			X				X					X
Height and Weight b	X b		X					X			X				X					X
Vital Signs	X	X	X	X	X	X	X	X	X	X	X	X	X	X	X	X	X	X	X	X
Complete Physical Exam	X																			X
Focused Physical Exam c			X		X		X		X		X		X		X		X			
Pulmonary Function Tests	X d		X e					X e			X e				X e					X e
CBC with Differential	X		X					X			X				X					X
Serum Chemistry	X		X					X			X				X					X
Spot Urine for Urinalysis	X		X					X			X				X					X
Pregnancy Test f	X		X		X	X	X	X	X	X	X	X	X	X	X	X	X	X	X	X
HRCT of Chest		X									X									X
12-Lead ECG	X										X									X
Serum and Plasma Biomarkers			X								X									X
Plasma HAHA			X																	
Whole Blood for DNA			X																	
AEs and SAEs g	X	X	X	X	X	X	X	X	X	X	X	X	X	X	X	X	X	X	X	X
Concomitant Medications h	X	X	X	X	X	X	X	X	X	X	X	X	X	X	X	X	X	X	X	X
Procedures and Nondrug Therapies	X	X	X		X	X	X	X	X	X	X	X	X	X	X	X	X	X	X	X
Study Drug infusion i			X		X	X	X	X	X	X	X	X	X	X	X	X	X	X	X	

Study Period	Screening Period (up to 6 weeks)		Treatment Period																	
	1	2 a	3	4	5	6	7	8	9	10	11	12	13	14	15	16	17	18	19	
Study Days			Day 1 pre dose	Day 1 post dose																
Study Week (± 3 day window for Week 3 to Week 48)	Scr 1	Scr 2 a	0	0	3	6	9	12	15	18	21	24	27	30	33	36	39	42	45	48
Subject Disposition			X i																	

Abbreviations: AE = adverse event; CBC = complete blood count; DLCO = diffusing capacity of the lungs for carbon monoxide; ECG = electrocardiogram; EX = extended (treatment); HAHA = human anti-human antibody; HCG = human chorionic gonadotropin; HRCT = high resolution computed tomography; SAE = serious adverse event; Scr = screening visit; SGRQ = Saint George’s Respiratory Questionnaire

- a Screening Visit 2 may be combined with Screening Visit 1.
- b Height will be measured only once at Screening Visit 1. Weight will be measured every 12 weeks to determine dose for the subsequent 12-week interval.
- c Including chest auscultation
- d Spirometry (DLCO at first screening test only).
- e Spirometry
- f Pregnancy tests (performed at Screening Visit 1, pre-dose Day 1, and pre-dose at other times) for women of childbearing potential only: serum pregnancy test at Screening Visit 1; urine pregnancy tests at other visits. A positive urine pregnancy test must be confirmed by serum HCG.
- g See Section 11.3.1 for follow-up of AEs.
- h Refer to Section 4.6.1 for prohibited concomitant medications.
- i Vital signs (blood pressure, pulse, respiration rate, and temperature) must be recorded prior to each FG-3019 infusion. Intra-infusion and post-infusion assessments will be performed according to Section 6.3.
- j Subjects who do not complete all visits in the Treatment Period will be encouraged to return for the assessments listed in Appendix 3.

**Appendix 2. Schedule of Assessments – Extended Treatment Phase**

Study Period	Treatment Period a																
	1-EX	2-EX	3-EX	4-EX	5-EX	6-EX	7-EX	8-EX	9-EX	10-EX	11-EX	12EX	13-EX	14-EX	15-EX	16-EX	17-EX
Visit Number	0- (Day 1-EX)	3-EX	6-EX	9-EX	12-EX	15-EX	18-EX	21-EX	24-EX	27-EX	30-EX	33-EX	36-EX	39-EX	42-EX	45-EX	48-EX
SGRQ					X				X				X				X
Weight b	X				X				X				X				X
Vital Signs	X	X	X	X	X	X	X	X	X	X	X	X	X	X	X	X	X
Complete Physical Exam																	X
Focused Physical Exam c			X		X		X		X		X		X		X		
Spirometry					X d				X d				X d				X d
CBC with Differential					X				X				X				X
Serum Chemistry					X				X				X				X
Spot Urine for Urinalysis					X				X				X				X
Pregnancy Test c	X	X	X	X	X	X	X	X	X	X	X	X	X	X	X	X	X
HRCT of Chest									X								X
12-Lead ECG									X								X
Serum and Plasma Biomarkers									X								X
AEs and SAEs f	X	X	X	X	X	X	X	X	X	X	X	X	X	X	X	X	X
Concomitant Medications g	X	X	X	X	X	X	X	X	X	X	X	X	X	X	X	X	X
Procedures and Nondrug Therapies	X	X	X	X	X	X	X	X	X	X	X	X	X	X	X	X	X
FG-3019 Infusion h	X	X	X	X	X	X	X	X	X	X	X	X	X	X	X	X	X
Subject Disposition	X i																
FOOTNOTES ARE ON THE FOLLOWING PAGE																	

- Abbreviations: AE = adverse event; CBC = complete blood count; ECG = electrocardiogram; EX = extended (treatment); FVC = forced vital capacity; HAHA = human anti-human antibody; HCG = human chorionic gonadotropin; HRCT = high resolution computed tomography; SAE = serious adverse event; SGRQ = Saint George's Respiratory Questionnaire.
- a The total duration of the study for subjects is indeterminate because subjects in the extension period may continue treatment until they meet stopping criteria (Section 4.2.3). Subjects who complete 48 weeks of treatment extension may continue treatment according to this table (beginning in Week 1Ex).
  - b Weight will be measured every 12 weeks to determine dose for the subsequent 12-week interval.
  - c Including chest auscultation
  - d Spirometry
  - e Pregnancy tests (performed pre-dose Day 1-EX and at other times) for women of childbearing potential only: urine pregnancy tests at all Extended Treatment Period visits. A positive urine pregnancy test must be confirmed by serum HCG.
  - f See Section 11.3.1 for follow-up of AEs.
  - g Refer to Section 4.6.1 for prohibited concomitant medications.
  - h Vital signs (blood pressure, pulse, respiration rate, and temperature) must be recorded prior to each FG-3019 infusion. Intra-infusion and post-infusion assessments will be performed according to Section 6.3.
  - i Subjects who do not complete all visits in the Treatment Period will be encouraged to return for the assessments listed in Appendix 3.

### Appendix 3. Schedule of Assessments – Early Termination/End of Treatment and Follow-up Visit

Assessment	Early Termination/End of Treatment a	End of Study
1. SGRQ	X b	
2. Vital Signs	X b	X
3. Complete Physical Exam	X b	
4. Spirometry	X b,c	
5. CBC with Differential	X b	
6. Serum Chemistry	X b	
7. Spot Urine for Urinalysis	X b	
8. Pregnancy Test d	X b	X
9. HRCT of Chest	X b	
10. 12-Lead ECG	X b	
11. Serum and Plasma Biomarkers	X b	
12. Plasma HAHA		X
13. AEs and SAEs e	X b,e	X b,e
14. Concomitant Medications f	X b	X
15. Procedures and Nondrug Therapies	X b	X
16. Subject Disposition	X	X

Abbreviations: AE = adverse event; CBC = complete blood count; ECG = electrocardiogram; HAHA = human anti-human antibody; HCG = human chorionic gonadotropin; HRCT = high resolution computed tomography; PFT = pulmonary function test; SAE = serious adverse event; SGRQ = Saint George's Respiratory Questionnaire.

- a End of treatment, including due to withdrawal/progression evaluation preferably 3 weeks after last dose of study drug for all subjects who have received more than 4 doses of FG-3019. The End of Study, final safety assessment should be 4 weeks after last dose of study drug. Study windows are  $\pm$  3 days
- b Subjects who completed the withdrawal/progression evaluations at Week 48 or for early withdrawal do not need to repeat them. Study endpoint evaluations do not require repetition if performed within 8 weeks, HRCT does not require repetition if performed within 4 months, and safety assessments, such as clinical laboratory tests, do not require repetition if performed within 2 weeks.
- c Spirometry .
- d Pregnancy tests for women of childbearing potential only: urine pregnancy tests at all Extended Treatment Period visits. A positive urine pregnancy test must be confirmed by serum HCG.
- e See Sections 4.7 and 11.3.1 for follow-up of AEs.
- f Refer to Section 4.6.1 for prohibited concomitant medications.

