#### **10.3.5 Safety Analyses**

Treatment-emergent adverse events (TEAEs), defined as new or worsening AEs that occur after the first dose of study drug and within 4 weeks of last dose of study drug, will be tabulated to examine their frequency, severity, organ systems affected and relationship to study treatment. Treatment emergent SAEs and TEAEs leading to study or treatment discontinuation will be listed or tabulated separately.

Clinically significant changes from baseline in vital signs, laboratory tests, physical examinations, and ECGs will be identified.

Human anti-human antibody data will be summarized in a separate report.

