## 11.3 Procedures for Eliciting, Recording, and Reporting Adverse Events

### 11.3.1 Adverse Event Reporting Period

The study period during which all AEs and SAEs must be collected begins after informed consent is obtained and ends 4 weeks after the last dose of study drug, except for pregnancy

reporting (Section 11.3.6). In addition, all AEs reported spontaneously by the subject to site personnel, outside the study period, may be recorded.

Adverse events will be followed until resolved, stable, or until the subject's last study visit or lost to follow-up. If an AE is not resolved or stabilized at the subject's last visit, it is up to the discretion of the Investigator and study Medical Monitor to determine if further monitoring of the event is warranted.

Adverse events collected prior to dosing of study drug will be considered "non-treatment emergent" while those reported after the first dose of study drug and up to 4 weeks after the last dose of study drug will be considered "treatment emergent" and will be assessed for relationship to study drug.

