### 11.3.2 Adverse Event Eliciting/Reporting

During the AE reporting period, study site personnel will query each subject at each visit to actively solicit any AE occurring since the previous visit. All AEs will be collected in response to a general question about the subject's well-being and any possible changes from the baseline or previous visit, but shall not be specifically solicited. There will be no directed questioning for any specific AE. This does not preclude the site from collecting and recording any AEs reported by the subject to site personnel at any other time.

Whenever possible, diagnoses should be recorded when signs and symptoms are due to a common etiology, as determined by qualified medical study staff. New indications for medications started after informed consent is obtained until 4 weeks after the last dose of study drug will be recorded as AEs; recurrence or worsening of medical history problems requiring new or changes in concomitant medication, will also be recorded as AEs. Abnormal, clinically significant laboratory results, physical examination findings, and ECGs will be recorded as AEs if they are deemed by the Investigator to meet criteria.

The following attributes must be assigned to each AE:

- Description (Investigator's verbatim term describing the event)
- Dates of onset and resolution
- Severity
- Relationship to study drug
- Outcome
- Action taken regarding study drug
- Other treatment required
- Determination of "seriousness"

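### Appendix 3 footnote b, read literally, lets sites skip the adverse-event query at End of Study, in conflict with the 4-week collection period and TEAE window

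*Protocol*

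**What the plan says.** Protocol Appendix 3 has two columns, Early Termination/End of Treatment and End of Study. The row "13. AEs and SAEs" carries superscripts b and e in both. In the End of Study column no other row has superscript b: vital signs, pregnancy test, HAHA, concomitant medications, procedures and disposition are plain entries.

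Footnote b can excuse an assessment in two ways relevant here. One has no time limit: "Subjects who completed the withdrawal/progression evaluations at Week 48 or for early withdrawal do not need to repeat them". The other is limited to two weeks: "safety assessments, such as clinical laboratory tests, do not require repetition if performed within 2 weeks".

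Footnote a sets the timing. End of Treatment is "preferably 3 weeks after last dose of study drug for all subjects who have received more than 4 doses of FG-3019". For the last visit, "The End of Study, final safety assessment should be 4 weeks after last dose of study drug". Both have windows of ±3 days. Footnote e sends the reader to Sections 4.7 and 11.3.1.

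The body of the protocol is unconditional. Under Section 11.3.1 the collection period "begins after informed consent is obtained and ends 4 weeks after the last dose of study drug". Under Section 11.3.2 "study site personnel will query each subject at each visit to actively solicit any AE occurring since the previous visit". Section 10.3.5 defines TEAEs as new or worsening events that "occur after the first dose of study drug and within 4 weeks of last dose of study drug". SAP Section 3.2.3 uses 28 days after the last infusion; for the randomised period it closes the window sooner if the first extension infusion comes first.

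**The concern.** A laboratory value from a week earlier can reasonably stand in for a new one. An AE query cannot, because its purpose is to find what has happened since the last time the subject was asked. A query on day 21 says nothing about an event that starts on day 24.

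Sites work from the schedule tables. A site that takes the superscript at face value would see the subject at End of Study, take vital signs and an antibody sample, and need not ask about adverse events. The TEAE tables would still present events as though they had been sought for the full 28 days after the last dose. Ascertainment in the final week would then depend on how each site read one footnote.

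**Working it through.** **1. The plan's own timing.** Infusions at Weeks 0, 3, ..., 45 make 16 doses. The last is at Week 45, and 45 + 4 = Week 49, the End of Study week given in Section 4.2.2. Week 48 is 3 weeks after the last dose, so the nominal gap is 49 − 48 = 1 week, or 7 days.

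**2. Gap from an in-window 3-week End of Treatment visit (Appendix 3, footnote a).** End of Treatment is at day 21 ± 3 after the last dose and End of Study at day 28 ± 3.
- Shortest gap: 25 − 24 = 1 day.
- Longest gap: 31 − 18 = 13 days.

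Every combination is inside 14 days.

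**3. Gap from Week 48.** Section 7.4 times scheduled visits from Day 1. Let d, w and e be the deviations (−3 to +3 days) of the Week 45 dose, the Week 48 visit and the End of Study visit.
- Gap = (315 + d + 28 + e) − (336 + w) = 7 + d + e − w.
- Range: 7 − 9 = −2 to 7 + 9 = 16 days. Values of zero or less are only a product of independent windows.
- The gap exceeds 14 days only when d + e − w is 8 (3 ways) or 9 (1 way), that is 4 of the 7 × 7 × 7 = 343 combinations.

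The 2-week waiver is therefore nearly always available from Week 48, with a few exceptions.

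**4. Early termination soon after the last dose.** If that visit falls fewer than 14 days after the last dose, a day-28 End of Study visit is more than 14 days later and the 2-week waiver does not apply. Only the untimed sentence of footnote b could then be invoked.

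**5. What goes unasked if the waiver is used.** The last query is nominally at day 21, leaving days 22 to 28.
- Share of the post-dose window: 7/28 = 25%.
- Share of the randomised observation period: 7/(315 + 28) = 7/343 = 2.0%.
- With windows, the Week 48 visit falls 21 + w − d = 15 to 27 days after the last dose, so 28 − 27 = 1 to 28 − 15 = 13 days are left.

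**6. The End of Study window itself.** Even with the query done, a visit at 28 − 3 = day 25 leaves days 26 to 28, up to 3 days of the TEAE window, with no scheduled query.

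**7. Who has these visits (illustration only).** All placebo completers are offered the extension (Section 4.2.3.3), and those who enter are queried at Day 1-EX (Appendix 2). FG-3019 completers qualify only with FVC % predicted above baseline (Section 4.2.3.2) or, if enrolled under the original protocol, a decrease below 3 points (Section 4.2.3.1). I assume a normal distribution with the Section 10.1 planning values, mean change −2.8 and SD 7.3.
- P(change > 0) = 1 − Φ(2.8/7.3) = 0.351.
- P(change > −3) = 1 − Φ(−0.2/7.3) = 0.511.
- So 49% to 65% of FG-3019 completers could not roll over, against none on placebo by rule.

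With the planned 10% dropout and no refusals, the proportion having an End of Study visit after the randomised phase is 0.1 + 0.9 × 0.649 = 0.684 (or 0.1 + 0.9 × 0.489 = 0.540) on FG-3019 and 0.1 on placebo. FG-3019 then supplies 0.684/0.784 = 87% (or 0.540/0.640 = 84%) of these visits. With assumed dropout of 10% to 30% and refusal of 0% to 30%, the share runs from 0.595 to 0.873. Neither assumed range comes from the documents.

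**The case against.** A reader might infer that active AE follow-up stops at three weeks by design. The documents do not support that. Section 4.2.1 keeps the 4-week safety assessment for all subjects, Section 11.3.2 requires a query at each visit, and footnote e in the same cell points to Section 11.3.1. A question about a new interval is arguably not a repetition at all, and the footnote's own example is laboratory tests. Superscripts b and e also appear together in the neighbouring cell, which is compatible with a copying slip. All of this stands. It makes the defect a conflict that could cause under-collection at some sites. It does not justify keeping the superscript: if it has no effect in that cell it only misleads, and if it has an effect it contradicts the body text.

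Other capture would also soften the loss. Concomitant medications are reviewed at End of Study, new medication indications up to 4 weeks are recorded as AEs (Section 11.3.2), spontaneous reports are recorded (Section 11.1), and deaths are reportable to 28 days (Section 11.3.5.2). An unasked week is therefore not the same as a week of lost events.

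A reader might also infer that the gap makes FG-3019 look safer. The roll-over rules make more End of Study visits on FG-3019 plausible, but no counts are given. The SAP rule closing the randomised-period TEAE window at the first extension infusion works the other way: a placebo subject who rolls over promptly could have that window close at about day 21, while an FG-3019 subject who does not roll over keeps 28 days. The direction of any net bias cannot be settled from the documents, and a count of missed events would need event rates they do not supply.

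**Conclusion.** The conflict is real and sits in an operative schedule table. The nominal 7-day gap places the last AE query within reach of footnote b for nearly all subjects who attend Week 48 or a 3-week End of Treatment visit on schedule. The exceptions are a few Week 48 timings and early-termination visits soon after the last dose. Where a site uses the waiver, about a quarter of the post-dose window and about 2% of the randomised observation period have no active query. That size assumes nominal visit timing and a literal reading of the footnote; how many sites would read it so is unknown. A difference between arms is possible but not established. The point warrants correction because it touches safety ascertainment and costs almost nothing to put right. It does not show that the planned safety comparison is biased.

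**What to change.** Delete superscript b from the AE/SAE cell in the End of Study column of Appendix 3, so that AEs and SAEs are always queried at that visit. Reword footnote b so that it agrees with Sections 11.3.1 and 11.3.2, for example by limiting its safety clause to laboratory tests and similar measurements.

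Separately, reconcile the ±3-day End of Study window with the 28-day TEAE window. Either a visit window that does not open before day 28 or a stated way of asking about days 26 to 28 after an early visit would do.

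The first change is one superscript and one sentence. The visit already takes place, so it adds no visit or procedure. The second is a change to a visit window or, at most, a short contact for subjects seen early.
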